6.3 Follow-up for toxicities

Patients who interrupt or permanently discontinue pasireotide due to an adverse event or abnormal laboratory value must be followed at least weekly for 28 days after the last dose of pasireotide, and subsequently at monthly intervals until resolution or stabilization of the event,

whichever comes first. If a patient requires a dose delay of > 21 days from the intended day of the next scheduled dose, then the patient should be discontinued from the study.

All patients will be followed for adverse events and serious adverse events for 28 days following the last dose of pasireotide.

6.3.1 Management Guidelines for Hyperglycemia

During the study, all patients with HbA1c $\geq 7\%$ and or fasting plasma glucose (FPG) > 130 mg/dL (7.2 mmol/L), should be considered for the following:

- Provided information and receive teaching on diabetes disease management
- Initiation of drug therapy with anti-hyperglycemic medications
- Referral to a diabetes specialist for evaluation and appropriate management
- Monitoring of blood glucose by fingerstick twice daily (fasting morning blood glucose and 2-hour post-meal) if not already done. Patients, who monitor blood glucose should keep a diary of their glucose values and present the collected data to their physician/diabetes specialist for evaluation and appropriate management.

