6.2 Permitted study drug adjustments

Toxicity will be assessed using the NCI-CTC for Adverse Events, version 4.0 (CTCAEv4.0, (<http://evs.nci.nih.gov/ftp1/CTCAE/About.html>)). For patients who are unable to tolerate pasireotide 60mg every 4 weeks, the dose may be changed to 40mg every 4 weeks (see table 6-2).

Table 6-2 Criteria for dose-modification of pasireotide

Adverse event	Action
*Grade \leq 2	No study drug adjustments
*Grade \geq 3 and judged as at least possibly drug related	
 • Reduce dose to 40mg • If AE improves to grade \leq2 before the next administration, increase dose to 60mg. If the dose is increased and that AE recurs at CTC grade \geq 3 the dose will be reduced back to the lower dose and shall not be increased again during the study period. • If AE does not improve to grade \leq2 on the lower dose before the next administration, the patient will discontinue the study drug and be followed for safety.

*This guidance should be use for all probably related AEs except for changes in blood glucose which should be addressed as described in Section 6.3.1 and changes in QTc interval which should be addressed as described in Section 6.3.2..
	

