7.1 Pretreatment Evaluation

Baseline tumor and patient characteristics including:

- Patient demographics: age, gender and race (Caucasian, Black, Hispanic, Asian, other).
- Medical history
- Medications
- ECOG performance status.
- Type of neuroendocrine tumor: primary site (if known) vs. unknown.
- Differentiation or grade (if available).
- Known sites of metastases.
- Estimation of tumor burden in the liver (none vs. <10% vs. >10%).
- Presence or absence of radiotracer uptake on OctreoScan (if available).
- Presence or absence of hormonal syndrome (carcinoid syndrome, gastrinoma syndrome, insulinoma syndrome, etc.)
- Presence or absence of a pathologically elevated hormone or biomarker.
- EORTC QLQ C-30 and EORTC QLQ GI-NET21 questionnaires

Tests to be performed within 28 days prior to initiation of therapy (if day 28 falls on a weekend or holiday the deadline may be extended to the next working day):

- Radiologic assessment of tumor burden by CT scan or MRI
- Assessment of secretory proteins. All patients will undergo an initial assessment of chromogranin A. Patients with suspected serotonin-producing tumors (and all patients with midgut carcinoid tumors) will have a 24 hour urine 5-HIAA measured at

baseline. Other possible neuroendocrine tumor markers/hormones (e.g. pancreatic polypeptide, gastrin, glucagon, etc.) may be collected at the discretion of the investigator based on clinical symptoms and tumor location.

Tests to be performed within 14 days prior to initiation of therapy (if day 14 falls on a weekend or holiday the deadline may be extended to the next working day):

- History and physical evaluation including height, weight, vital signs and performance status.
- Baseline hematological and biochemical profiles including CBC with differential and comprehensive metabolic panel (fasting glucose, sodium, potassium, chloride, bicarbonate, creatinine, blood urea nitrogen, albumin, SGOT (AST) SGPT (ALT) total bilirubin, alkaline phosphatase, calcium and magnesium).
- Hemoglobin A1c
- Serum pregnancy test for women of childbearing potential
- Electrocardiogram

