7.2 Evaluations During Treatment

Beginning of every cycle (defined as 28 days +/- 3 days) (every 6 months after 5 years on therapy)

- Physical examination
- Toxicity assessment
- Vital signs
- ECOG performance status
- CBC with differential
- Fasting comprehensive metabolic panel
- Assessment of adverse events

Data to be obtained every 3 cycles of treatment (every 12 months after 5 years on therapy):

- Radiologic assessment of tumor burden by CT scan or MRI. Patients who have been on study for > 2 years will undergo scans every 6 cycles. Patients who have been on study for > 5 years will undergo scans every 12 cycles, at treating physician discretion.
- Electrocardiogram (baseline, 6 hours after 1st injection, 21 days after 1st injection, 21 days after 3rd injection, Cycle 6, and every 3 cycles thereafter.)
- Liver function testing 21 days after 1st injection and 21 days after 3rd injection
- Assessment of chromogranin A and/or other tumor markers or hormones if elevated at baseline (see section 7.1).
- EORTC QLQ C-30 and EORTC QLQ GI-NET21 questionnaires

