7.3 End of Treatment Evaluation

Data to be obtained at completion of study:

- Physical examination
- Toxicity assessment
- Vital signs
- Weight
- ECOG PS
- CBC with differential
- Comprehensive metabolic panel
- Glycosylated hemoglobin
- ECG
- Assessment of adverse events
- Radiologic assessment of tumor burden (if patient is discontinued for any reason other than radiographic disease progression).

Table 7-3 lists all of the assessments and indicates the visits at which they are to be performed with an “X”. All data obtained from these assessments must be supported in the patient’s source documentation.

Table 7-3 Visit evaluation schedule

Evaluation	Screening/ Baseline^a	6 hours after 1st injection, 21 days after 1st and 3rd injections	Each Cycle (day 1)^k	Cycle 6	Every 3 Cycles	End^b
Informed consent	X					
Demographics	X					
Relevant medical history/ current medical conditions	X		X			X
Diagnosis and extent of cancer	X					
Physical exam	X		X			X
Vital signs	X		X			X
ECG ^c	X	X		X	X	X
LFT testing		X				
ECOG Performance Status	X		X			X
CBC with differential ^d	X		X			X
Glycosylated hemoglobin	X					X
Fasting	X		X			X

Comprehensive metabolic panel ^e						
Pregnancy test and review of contraception ^f	X					X
Secretory hormones ^g and serum chromogranin A	X				X	
Radiologic assessment of tumor burden ^h	X				X	X
Adverse events ⁱ	X		X			X
Concomitant medications ^j	X		X			X
EORTC QLQ C-30 and EORTC QLQ GI-NET21 questionnaires	X				X	

^a Screening includes review of: demography/informed consent, inclusion/exclusion criteria, relevant medical history/concomitant medications, diagnosis and extent of cancer.

^b Patients who interrupt or permanently discontinue pasireotide due to an adverse event or abnormal laboratory value must be followed at least weekly for 28 days after the last dose of SOM230, and subsequently at monthly intervals until resolution or stabilization of the event, whichever comes first.

^c All ECGs should be done before SOM230 injection on the same day. ECG should be done at any time when clinically indicated.

^d Complete blood count must include: hemoglobin, hematocrit, platelets, total white blood cell count and differential.

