^e Comprehensive metabolic panel should include fasting glucose, sodium, potassium, chloride, bicarbonate, creatinine, blood urea nitrogen, albumin, total protein, SGOT (AST), SGPT (ALT), total bilirubin, alkaline phosphatase, calcium and magnesium. Patients are to fast overnight for 8 hours prior to all biochemistry samples being taken. Blood samples are to be taken in the morning. Water is allowed during this time. Clinically significant electrolyte abnormalities are to be addressed prior to each SOM230 administration.

^f For women of child-bearing potential: Women of childbearing potential must have a negative serum pregnancy test within 14 days of enrollment. Acceptable contraception must be used while on study and for at least 60 days after last dose of pasireotide.

^g If patients present with hormonally active tumor, secretory hormone levels corresponding to the syndrome (e.g. urine 5-HIAA, gastrin, glucagon, insulin, etc.) should be measured at baseline and each restaging cycle.

^h Baseline radiologic tests (CT or MRI with iv contrast) should include all known sites of metastatic disease. For most midgut carcinoid tumors, a CT or MRI scan of the abdomen and pelvis is indicated. For pancreatic neuroendocrine tumors, a CT or MRI scan of the abdomen may be sufficient. Patients who have been on study for > 2 years will undergo scans every 6 cycles. Patients who have been on study for > 5 years will undergo scans every 12 cycles.

ⁱ See section 9.1 for definitions of adverse events

^j All concomitant medications, including over the counter drugs, should be documented each visit. Particular attention should be paid to dose of diabetic medications. Patients with diabetes are to be instructed to check blood glucose levels via a fingerstick several times daily, particularly for the first few days of treatment.

^k For patients who have been on study for >5 years, all procedures, with the exception of vitals and treatment administration, will occur only once every 6 months (EP, labs, EKGs, questionnaires); scans will occur once every 12 months.

8 Outcome Measures

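### The HbA1c part of the Section 6.3.1 hyperglycemia trigger has no scheduled value while the patient is on pasireotide

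*Combined protocol and SAP*

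**What the plan says.** Section 6.3.1 sets a trigger with two limbs, either of which is enough. It begins "During the study, all patients with HbA1c" at or above 7% and adds, joined by and/or, FPG above 130 mg/dL. The response is worded as something to be considered. One of its items is "Monitoring of blood glucose by fingerstick twice daily (fasting morning blood glucose and 2-hour post-meal) if not already done".

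The schedule for the two measurements is as follows.

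- Before therapy: Section 7.1 lists "Hemoglobin A1c" among the tests within 14 days of starting.
- During therapy: the every-cycle list in Section 7.2 has "Fasting comprehensive metabolic panel", which includes fasting glucose (Table 7-3, footnote e). Neither that list nor the every-3-cycles list names HbA1c.
- At the end: Section 7.3 lists "Glycosylated hemoglobin". Table 7-3 marks that row only under Screening/Baseline and End.

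The footnote to Table 6-2 exempts from the general dose rule "changes in blood glucose which should be addressed as described in Section 6.3.1". Section 6.4 separately withdraws patients with uncontrolled diabetes mellitus, without naming a test or a threshold.

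**The concern.** A threshold that applies throughout the study needs a measurement taken throughout the study. A site that follows the schedule exactly will have one HbA1c before the first injection and the next when the patient is leaving treatment. The second comes too late to prompt management during treatment.

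This matters for the drug in question. Section 1.4.1 reports that HbA1c rose by about 1% with the subcutaneous form, corresponding to about 30 mg/dL of glucose, with larger rises at higher doses. The trial starts at 60 mg, the highest LAR dose it allows (Section 2.1). Because Table 6-2 sends glucose changes to Section 6.3.1, that section carries the management of an expected toxicity. Without a scheduled test, each site must decide for itself whether to order HbA1c.

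**Working it through.** The documents state no figure to reproduce on this point. The check sets the trigger against the schedule, then counts measurements and sizes the remedy.

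**1. Scheduled measurements per limb.** Cycles are 28 days (Section 4.1).

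| Measure | Before therapy | During cycles, year 1 | End |
|---|---|---|---|
| Fasting glucose | 1 | 365/28 = 13.0 | 1 |
| HbA1c | 1 | 0 | 1 |

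The lists in Sections 7.1 to 7.3 agree with Table 7-3, and no footnote adds an on-treatment HbA1c.

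**2. Who is already covered.**

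- Anyone whose FPG exceeds 130 mg/dL at a cycle visit: one limb is enough.
- Patients entering with HbA1c of 7% to 8%: exclusion criterion 3 removes only those above 8%, and the screening value already meets the trigger.
- Patients with known diabetes: under footnote j, "Patients with diabetes are to be instructed to check blood glucose levels via a fingerstick several times daily".

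**3. Who is left.** Patients without known diabetes whose HbA1c goes from below 7% to 7% or more on drug while FPG stays at or below 130 mg/dL. Their scheduled chemistry cannot show a post-meal rise, because "Patients are to fast overnight for 8 hours prior to all biochemistry samples being taken". The post-meal fingersticks in Section 6.3.1 begin only once its trigger has been met.

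**4. Does the arithmetic leave room for such patients?** Take the Section 1.4.1 ratio of 30 mg/dL per HbA1c point and assume, at the strict end, that the whole rise appears in fasting glucose. For a rise of d points, a patient is missed if baseline HbA1c is at least 7 − d and below 7, and baseline FPG is at most 130 − 30d.

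| d (assumed) | Baseline HbA1c | Baseline FPG |
|---|---|---|
| 0.5 | 6.5% to below 7% | at most 115 mg/dL |
| 1.0 | 6.0% to below 7% | at most 100 mg/dL |
| 1.5 | 5.5% to below 7% | at most 85 mg/dL |

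If only part of the rise shows in fasting samples, the FPG ceiling moves up towards 130 mg/dL. The cells show that the FPG limb does not logically include the HbA1c limb. They do not measure impact: the documents give no baseline distribution of either variable, so no patient count follows.

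**5. Extra assays if HbA1c is added every 3 cycles (84 days).** Rate on treatment: 365/84 = 4.3 per year. Section 11.2 gives median PFS of 5 months (null) and 9 months (alternative). Exponential PFS reproduces its 12-month rates: 0.5^(12/5) = 0.19 and 0.5^(12/9) = 0.40. Assume patients stop only for a PFS event and count the first 5 years (21 assessments). With r = 0.5^(84/median in days), expected assays per patient = r(1 − r^21)/(1 − r).

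- Median 5 months (about 152 days): r = 0.682, giving 2.14 per patient and 2.14 × 35 = 75 in all.
- Median 9 months (about 274 days): r = 0.8085, giving 4.17 per patient and 4.17 × 35 = 146 in all.

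The multiplier 35 is the enrolment figure in Section 11.1.

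**The case against.** The best case for leaving the schedule alone is that fasting glucose every cycle is a defensible way to monitor, and that Section 6.3.1 is advisory. Several parts of this stand. The FPG limb is tested about monthly. An investigator may order HbA1c at any time. Section 1.4.1 says that glucose rises appeared more marked in patients with a history of hyperglycemia or diabetes, so the group left uncovered is probably the less affected one. The 1% figure comes from the subcutaneous form. With the LAR form in healthy volunteers, Section 1.4.2.1 describes mild, asymptomatic fasting rises that generally resolved within 3 to 4 weeks of the injection.

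It can also be said that the HbA1c limb does have inputs, because the trigger covers the whole study and the screening value falls within the plan. That is true for patients who enter at 7% or more. It does nothing for a patient who crosses 7% on drug, which is the case a toxicity guideline exists to catch.

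A reader might infer two stronger things. One is that Section 6.3.1 is the only glucose safeguard; the documents do not support this, because Section 6.4 provides for withdrawal for uncontrolled diabetes and Section 9.1 requires adverse events to be sought at each visit. The other is that hyperglycemia goes unmonitored during treatment; the per-cycle fasting panel rules that out.

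**Conclusion.** The inconsistency is real and plain on the text: one of the two limbs of a trigger that applies during the study has no scheduled value between screening and the end of treatment. Its reach is limited to patients without known diabetes whose HbA1c reaches 7% on drug with FPG at or below 130 mg/dL. How many there would be cannot be derived from the documents.

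This is a safety-monitoring point and a cheap improvement that the sponsor could make. It involves no estimand, test or analysis set, and PFS and the sample size are untouched. The finding on the schedule rests on no assumption. The assay count assumes exponential PFS, the protocol's two medians, and stopping only for a PFS event; earlier stopping for toxicity would lower it.

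**What to change.** Add HbA1c to the every-3-cycles list in Section 7.2 and to the Every 3 Cycles column of Table 7-3. State explicitly that after 5 years it is measured every 6 months with the other laboratory tests, as footnote k provides. The wording is needed because the heading of that list in Section 7.2 says every 12 months after 5 years, so an unqualified addition would carry two different frequencies.

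The cost is about 2 to 4 assays per patient, taken at visits where the fasting panel is already drawn, with no new visit. Somewhat more patients would be flagged for glucose management.

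If the sponsor does not want the assay, Section 6.3.1 should say that the HbA1c limb refers to the screening value and that FPG alone is the on-treatment trigger. That removes the inconsistency at no assay cost but leaves the small group above undetected.

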6.3.2 Management Guidelines for QTc prolongation on ECG

Table 6-3-2 provides guidelines for management of prolonged QTc interval.

Table 6-3-2 Guidelines for Management of QTc Prolongation

QTc CTC grade 1 (≤ 480 msec)	No study drug adjustments
QTc CTC grade 2 (> 480 or ≤ 500 msec) either drug related or drug unrelated	Patient is to be referred to a cardiologist for evaluation and appropriate management, and the patient can remain in the study Patient's study drug dose will be reduced to 40 mg.
QTc CTC grade ≥ 3 (> 500 msec), or increase in QTcF ≥ 60 ms over baseline	Discontinue study drug Follow patient for safety

6.3.3 Management Guidelines for Abnormal Liver Function

Table 6-3-3: SOM230 Abnormal liver function management

Perform within **72 hours** of awareness of abnormal LFTs:

- Perform liver-directed medical history and physical examination (i.e. assess occupational hazards, concomitant medications including OTC meds, intercurrent illness, etc)
- Liver chemistry tests: ALT, AST, total bilirubin, (fractionate to direct/indirect bilirubin if total bilirubin is $> 2.0x$ ULN), Alb, PT (INR), ALP, and GGT
- Perform hepatitis screen: anti-HAV, IgM (to confirm acute hepatitis A), HbsAg, Anti-HBc, anti-HCV (if positive PCR viral load should be assessed), Anti-HEV, ANA antibodies, anti-smooth muscle anti-bodies, CMV, EBV
- Perform abdominal ultrasound (liver and biliary tree)
- Collect PK sample and record the dose level and the dosing time for the last dose the patient has taken prior to PK sampling.

Liver chemistry tests should be monitored **every 3-4 days** for s.c. and LAR studies until resolution or return to baseline status.

For ALT or AST > 5x ULN and ≤ 8x ULN:

Study medication should be temporarily interrupted and liver chemistry tests monitored **every 3-4 days** for s.c. and LAR studies until resolution or return to baseline

If resolution or return to baseline does not occur after 2 weeks, the patient should be discontinued.

If ALT or AST returns to less than 5x ULN, study drug can be resumed and patient can continue study per protocol

If ALT or AST rises above 5x ULN anytime after study drug is resumed, then study drug should be discontinued immediately.

Table 6-3-3-1: SOM230 Abnormal liver function discontinuation criteria Hepatic-related discontinuation criteria for all ongoing studies

Study medication should be discontinued immediately if any of the discontinuation criteria below are met:

ALT or AST > 3x ULN and Total Bilirubin > 2x ULN and ALP < 2x ULN

ALT or AST > 5x ULN and ≤ 8x ULN persistent for more than 2 weeks

ALT or AST > 8x ULN

Re-challenge of study medication is prohibited once discontinuation criteria are met.

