5.1.1 Inclusion criteria

1. Locally unresectable or metastatic carcinoid or pancreatic neuroendocrine tumors.
2. Tumors must be considered well or moderately differentiated (or low to intermediate grade). Patients with poorly differentiated neuroendocrine carcinomas or small cell carcinomas are excluded from the study.
3. No prior systemic antineoplastic neuroendocrine tumor treatment (including prior somatostatin analogs). However patients who have received a short course of SQ octreotide (<10 days) in the past are eligible if > 1 week has elapsed from their last octreotide injection.
4. Age \geq 18 years.
5. Minimum of four weeks since any major surgery.
6. Measureable disease by RECIST.
7. ECOG performance status \leq 1
8. Life expectancy 12 weeks or more.
9. Adequate bone marrow function as shown by: ANC \geq $1.0 \times 10^9/L$, Platelets \geq $75 \times 10^9/L$, Hgb $>$ 8 g/dL.
10. Adequate liver function as shown by: serum bilirubin \leq 2.0 x upper limit of normal (ULN), and serum transaminases activity \leq 2 x ULN, with the exception of serum transaminases ($<$ 3 x ULN) if the patient has liver metastases.
11. Adequate renal function as shown by serum creatinine \leq 2.0 x ULN.

12. Fasting serum cholesterol ≤ 300 mg/dL OR ≤ 7.75 mmol/L AND fasting triglycerides ≤ 2.5 x ULN. NOTE: In case one or both of these thresholds are exceeded, the patient can only be included after initiation of appropriate lipid lowering medication.
13. Women of childbearing potential must have a negative serum pregnancy test within 14 days of the administration of the first study treatment. Women must not be lactating. Both men and women of childbearing potential must be advised of the importance of using effective birth control measures during the course of the study.
14. Signed informed consent to participate in the study must be obtained from patients after they have been fully informed of the nature and potential risks by the investigator (or his/her designee) with the aid of written information.

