Appendix E: Pasireotide LFT management algorithm

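### Minor wording faults in the safety rules: read literally, the two-week liver stop conflicts with the resume line below 5x ULN; the QTc grade 2 range is misprinted; relatedness triggers differ

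*Combined protocol and SAP*

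**What the plan says.** **Liver (Section 6.3.3).** For ALT or AST above 5x and up to 8x ULN the plan begins with an interruption: "Study medication should be temporarily interrupted and liver chemistry tests monitored" every three to four days. Two lines then decide what follows:

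- Stop: "If resolution or return to baseline does not occur after 2 weeks, the patient should be discontinued".
- Resume: "If ALT or AST returns to less than 5x ULN, study drug can be resumed and patient can continue study per protocol".

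Table 6-3-3-1 lists the immediate stops. The one aimed at this range is "ALT or AST > 5x ULN and ≤ 8x ULN persistent for more than 2 weeks". Values above 8x also stop the drug, as does the combination "ALT or AST > 3x ULN and Total Bilirubin > 2x ULN and ALP < 2x ULN". Section 5.1.1, item 10, caps transaminases at entry at 2x ULN, or below 3x with liver metastases. The last page carries the title "Appendix E: Pasireotide LFT management algorithm", but its content is not in the text available to us.

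**QTc (Section 6.3.2, Table 6-3-2).** Grade 1 is at or below 480 msec, with no change of dose. Grade 2 is printed as above 480 *or* at or below 500 msec, with cardiology referral and 40 mg. Above 500 msec the drug is discontinued.

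**Relatedness (Sections 6.2 and 6.3.5).** The row of Table 6-2 for adverse events of grade 3 or higher begins with "Reduce dose to 40mg" and applies to events judged *at least possibly* related. The footnote to the same table says *probably* related, and sets aside only glucose and QTc. Section 6.3.5 says *directly attributable* and sends the reader to Table 6-2 for the action.

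**The concern.** These are operative rules for stopping, reducing or continuing the drug, applied by several institutions. Section 1.4 reports liver enzyme rises and a suggested QTcF effect with pasireotide, so the situations are foreseeable. Where the text gives two answers, two sites can each follow the protocol and treat the same patient differently. Either error matters to that patient: one reading takes a recovering patient off treatment, and the other gives a further depot injection, which cannot be taken back, to someone whom the stop line would have withdrawn.

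**Working it through.** The plan states no figure on this point, so the check is to apply each rule to the same cases.

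**1. Liver.** Inputs: the stop line, the resume line and the persistence criterion in Table 6-3-3-1 (all Section 6.3.3), and the entry limits (Section 5.1.1, item 10). *Resolution* is read literally as return to normal. Take a baseline of 1x ULN, a peak of 6x and no bilirubin rise:

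| ALT/AST at two weeks | Stop line | Resume line | Table 6-3-3-1 |
|---|---|---|---|
| 1x | no stop | may resume | no stop |
| 4x | stop | may resume | no stop |
| exactly 5x | stop | may not resume | no stop |
| 6x | stop | may not resume | stop |

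The conflict is in the 4x row. In general:

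disputed range = above baseline and below 5x ULN; width = 5 − baseline (in multiples of ULN)

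- Baseline 1x: 1x to 5x, width 5 − 1 = 4.
- Baseline 2x (entry limit): 2x to 5x, width 5 − 2 = 3.
- Baseline just under 3x (entry limit with liver metastases): about 3x to 5x, width 5 − 3 = 2.
- If *resolution* means below 5x: width 5 − 5 = 0.

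Because baseline is below 3x for every eligible patient, two-week values from 3x to below 5x are disputed for all of them on the literal reading. The exception is a patient who also meets the bilirubin and ALP criterion, since Table 6-3-3-1 already stops that patient. Exactly 5x is a separate small gap: it is too high to resume and too low for the table's stop.

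Which meaning of *resolution* fits better? Section 6.3.3 uses the same phrase earlier to say when monitoring of any abnormal liver test ends. If it meant below 5x, a patient whose value never exceeded 4x would need no monitoring. The resume line also states its 5x limit in different words. The reading below 5x is therefore possible but strained.

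**2. QTc.** Any value at or below 500 meets the second printed limit, and any value above 500 meets the first. With *or*, all 301 whole values from 300 to 600 msec are grade 2. With *and*, only 481 to 500 are: 500 − 480 = 20 values, which fit between the neighbouring rows without overlap.

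**3. Relatedness.** For one grade 3 event:

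| Investigator's judgement | Table 6-2 row | Footnote | Section 6.3.5 |
|---|---|---|---|
| possibly related | act | outside | outside |
| probably related | act | act | unclear |
| directly attributable | act | act | act |

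The three places agree only in the last line.

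**The case against.** The strongest reply is that *resolution* is offered as an alternative to return to baseline, so it may well mean something less. The resume line and Table 6-3-3-1 both turn on 5x, and reading *resolution* as below 5x reconciles all three. Appendix E is titled as the liver algorithm and may say so. This stands as far as it goes: the conflict is one of literal reading, not a proven contradiction, and Appendix E has to be checked first. It does not explain why the same phrase ends monitoring for all liver abnormalities.

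It is also fair that the neighbouring QTc rows show what was meant, and that Section 6.3.5 defers to Table 6-2, whose row is the natural trigger. Both points lower the risk, but the text still needs correcting.

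A reader might go further than the documents allow in five ways:

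- *Every rise above 5x falls under both Table 6-2 and Section 6.3.3.* The footnote does not exempt liver events. But the CTCAE limits for ALT and AST are not in the documents, and Section 9.1 counts a laboratory value as an adverse event only if it causes symptoms, is clinically significant or needs therapy. The overlap is conditional. What remains is that no resumption dose is stated.
- *The clause on a QTcF rise of 60 ms or more contradicts the absolute limits.* It sits in the discontinue row, joined by *or*, and works as an independent stop.
- *Liver stops are lost because the list in Section 6.4 omits them.* Section 6.3.5 sends liver discontinuation to Section 6.3.3.
- *The suspected/not suspected scale in Section 9.1 is a further conflicting trigger.* It is a category for recording events.
- *The primary result is distorted, because Table 8.4 censors at the last scan when treatment stops for toxicity.* Nothing in the documents says how often the disputed cases arise, so no such effect can be claimed.

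**Conclusion.** The point holds as a minor one. Three operative safety rules conflict or are misprinted.

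- The liver conflict is the substantive part. On the literal reading it covers two-week values above baseline and below 5x ULN, a band 2 to 4 multiples of ULN wide for the baselines shown. It vanishes if *resolution* means below 5x. The conclusion assumes that Appendix E does not already define the term; if it does, Section 6.3.3 should still be worded to match.
- The QTc misprint is an evident slip with small clinical risk.
- The relatedness wording leaves the action unclear only for grade 3 or higher events judged related but short of directly attributable.

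Several outcomes stay clear on any reading: values above 8x or persisting above 5x beyond two weeks stop the drug, a return to baseline within two weeks allows it to continue, and a QTc above 500 msec stops it. No sample size, test or error rate is touched, and no effect on progression-free survival is claimed.

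**What to change.** - **Liver.** First compare Section 6.3.3 with Appendix E. If the 5x boundary is what was intended, replace the stop and resume lines with: discontinue if ALT/AST is still ≥5x ULN after 2 weeks; resume only if <5x ULN within that window, at a stated dose. Use the same ≥5x boundary in the persistence criterion of Table 6-3-3-1, so that exactly 5x is assigned. State that Section 6.3.3 governs liver enzyme rises in place of Table 6-2. If Appendix E instead requires return to baseline, align the resume line and the table with that stricter rule.
- **QTc.** In Table 6-3-2, print grade 2 as > 480 *and* ≤ 500 msec.
- **Relatedness.** Use one trigger, *at least possibly related*, in the Table 6-2 row, its footnote and Section 6.3.5.

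The cost is the wording of a protocol amendment. It adds no visits, tests or patients.
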